1. SYNOPSIS

Study Title	Evaluation of a new 6 minute walk test smartphone app in patients with pulmonary arterial hypertension (the 6-APP Study)	
Internal ref. no. / short title	6-APP Study	
Study Design	Comparison of standard 6 minute walk test with 6 minute walk test smartphone app	
Study Participants	Patients with, or being assessed for, pulmonary hypertension	
Planned Sample Size	30	
Planned Study Period	Q4 2017- Q4 2019	
	Objectives	Outcome Measures
Primary	To demonstrate that patients are able and willing to use the app for the 6MWT	Percentage of participants who perform app-based home 6MWT
Secondary	
To validate app 6MWT measurements against the hospital 6MWT
 
To compare the outdoor 6MWT app with the hospital based 6MWT
 
To assess the usability and acceptance of the app and the physicians' website
	
Average and standard deviation of the difference in distance as measured by physiologists and the app
 
Correlation of outdoor 6MWT app parameters with the hospital 6MWT test.
 
Standard usability and acceptance questionnaires, semi structured interviews, analysis of technical logs

2. ABBREVIATIONS

CI	Chief Investigator
CRF	Case Report Form
GCP	Good Clinical Practice

Principal Investigator:

[name]

Short Title:

6-APP Study

Ethics Ref:

insert

GP	General Practitioner
ICF	Informed Consent Form
NHS	National Health Service
NRES	National Research Ethics Service
NYHA class	New York Heart Association class
PAH	Pulmonary arterial hypertension
PI	Principal Investigator
PIL	Participant/ Patient Information Leaflet
R&D	NHS Trust R&D Department
REC	Research Ethics Committee
SOP	Standard Operating Procedure
VO2 Max	Maximal oxygen consumption on exercise test
6MWT	Six minute walk test

3. BACKGROUND AND RATIONALE

Pulmonary Arterial Hypertension (PAH) is a progressive illness that; if not diagnosed early or left untreated, can be a severe life limiting condition (1). It is a chronic disease of the pulmonary vasculature, with vascular proliferation and remodelling of the small pulmonary arteries leading to a progressive increase in pulmonary vascular resistance (PVR). This can ultimately lead to right heart failure and premature death (2). The predominant symptom of PAH is dyspnoea on exertion, with a decrease in exercise capacity, and most patients present with this symptom (2).

PAH is an uncommon condition, affecting about 6000 patients in the United Kingdom (3), and due to its rarity, the NHS commissions 7 centres to care for patients with PAH (4). Oxford University Hospital works closely with the Royal Brompton Hospital to provide care for patients with PAH in Oxfordshire and the surrounding region.

The six-minute walk test (6MWT) is a standard method for measuring exercise capacity in patients with cardiopulmonary disease such as PAH. The 6MWT measures how far a patient can walk in 6 minutes. Walking is an activity performed every day, by most patients except for those most severely limited. By assessing patients' ability to exercise, the 6MWT provides a global assessment of respiratory, cardiovascular, neuromuscular and cognitive function. The 6MWT does not differentiate what limits the patient, nor does it assess maximal exercise capacity. Instead, the 6MWT allows the patient to exercise at a daily functional level, and is a useful tool for assessing changes after a therapeutic intervention, and correlates with a subjective improvement in dyspnoea (5).

In PAH the 6MWT is used to evaluate patients' response to treatment, with an increase in 6MWT distance of greater than 42 m being considered a clinically significant improvement (6). Furthermore,

Principal Investigator:

[name]

Short Title:

6-APP Study

Ethics Ref:

insert

change in 6MWT distance correlates with VO2 max, NYHA class and mortality in PAH patients, (7) providing an objective assessment of disease progression, prognosis and response to treatment. It is a universally accepted test as it is safe and easily performed by the patient.

The 6MWT has become the primary end-point for many trials, and as a surrogate invalidated survival outcome for all placebo controlled trials of PAH therapy (8). It is used by regulatory bodies to determine whether a treatment should be approved. However, there is much discrepancy between whether it is the total distance walked at baseline prior to treatment, a decrease in total distance walked over time or a percentage increase in walking distance that correlates best with survival outcome. We hypothesize that it is all 3 of these measures, and that having a validated and more reproducible 6MWT would help assess patients and guide treatment strategies better.

The test is usually performed in hospital, by walking along a hospital corridor, where many factors on the day of the test can affect patients' performance, including tiredness, unfamiliarity with the environment or anxiety. The test typically requires 2 physiologists to monitor the distance walked by the patient, their oxygen saturations by pulse oximetry, and to record symptoms felt during the test. To improve the assessment of a patient's exercise capacity using a 6MWT, we hypothesized that the test would reflect more the patient's functional status, if it were undertaken prior to the hospital outpatient appointment. We have designed a mobile-phone "app" that allows patients to perform the 6MWT within the patient's home environment. This is felt to be more appealing to the patients, and would reduce the time spent in hospital on the day of their outpatient appointment.

The 6MWT app is categorised as mobile-health (m-health) system, a form of telehealth whereby healthcare is delivered at a distance using smartphones. By utilizing biometric collection devices such as a pulse oximeter monitor with Bluetooth capability, m-health can be used to measure the oxygen saturation levels in the blood from patients, and transmit them to a secure server, allowing them to be reviewed by cardiologists and other healthcare professionals.

The evidence-base for m-health as a tool for assessing physical fitness is increasingly established (9, 10). This new approach not only offers the opportunity for reliable collection of data, but provides the infrastructure to do this at scale and will allow decisions on patient's health to be based on more frequent and more accurate information.

There are no known risks to undertaking a 6MWT in the community as walking is an activity of daily living, and all patients are encouraged to walk daily.

The population to be studied would be those with PAH who are currently assessed with a 6MWT. Once the app has been validated, patients with any type of cardiorespiratory disease who are assessed with a 6MWT could use the app, for example patients with chronic obstructive airways disease, heart failure, renal failure, pre-transplantation work up.

The 6MWT results form part of the NHS data set collected by NHS England for patients with PAH, and it would be beneficial to have a more reproducible assessment, whose results can be compared between the 7 centres providing care for these patients. At present, there is much variability in how 6MWTs are performed between units, and the app would reduce this variability.

Principal Investigator:

[name]

Short Title:

6-APP Study

Ethics Ref:

insert

The 6MWT has been undertaken at the JR for 5 years and we would like to retrospectively analyse the data from the 6MWT that have previously been undertaken. The data on patients will be pseudo-anonymised, i.e. no personal information like name, surname or address, will be used, but we will keep date of birth, gender, diagnosis, dates and results of the 6MWT, date and causes of death. As part of the clinical care team reviewing the data is part of the normal standard of care for patients with PHT. The data is collected on the Solus cardiac reporting system and can be extracted from this database and the data will be pseudo-anonymised by the PI for analysis, and then shared with the wider research team. The data would be analysed to look at distance walked, and change in Oxygen saturation and heart rate during the test. We would analyse the data over time, to look for changes in these parameters and correlate these with outcome data, ie mortality. The data would be anonymised when reviewed.

4. OBJECTIVES AND OUTCOME MEASURES

Objectives	Outcome Measures	Timepoint(s) of evaluation of this outcome measure (if applicable)
Primary Objective O1: To demonstrate that patients are able and willing to use the app for the 6MWT	Percentage of participants who perform app-based home 6MWT	TP 1: 3 months after baseline visit TP 2: 6 months after baseline visit
Secondary Objectives O2: To validate app 6MWT measurements against the hospital 6MWT. O3: To compare the outdoor 6MWT app with the hospital based 6MWT.	Average and variability of the difference in distance as measured by physiologists and the app. Correlation of outdoor 6MWT app parameters with the hospital 6MWT test.	TP 1: at baseline visit TP 2: at 3-month visit TP 3: at 6-month visit TP 1: baseline visit 6MWT compared with following home test TP 2: 3-month visit 6MWT compared with closer home test before or after TP 3: 6-month visit 6MWT compared with closer home test before or after

Principal Investigator:

[name]

Short Title:

6-APP Study

Ethics Ref:

insert

O4: To assess the usability and acceptance of the app and the physicians' website.	Standard usability and acceptance questionnaire to users assessing their use of the app and website, semi structured interviews, analysis of technical logs.	TP 1: at 6 months after baseline visit
Tertiary Objectives	O5: To test whether the 6MWT app can detect changes in 6MWT distance more effectively than the hospital 6MWT, in patients starting advanced therapies.	Comparison of change in 6MWT app measurement with hospital 6MWT measurement, measured before and after initiation of new therapies.

5. STUDY DESIGN

We propose to evaluate a novel approach to service delivery by monitoring PAH patients using an established m-health system to send 6MWT results to a central server where they can be accessed by the clinical team (Figure 1). The system includes a mobile phone “app” to allow participants to comfortably perform the 6MWT at home (indoors or outdoors). In the outdoor scenario, the app makes use of GPS to track the user’s position. In the indoor scenario it uses the phone’s accelerometer and magnetometer (compass) to count the number of laps over a fixed-length walkway.

[figure not shown]
Figure 1. Diagram of the system

Principal Investigator:
Short Title:

[name]
6-APP Study

Ethics Ref:

insert

Undertaking a 6MWT test within the participant's home environment, using mobile technology to transmit the results via a software application on a mobile phone is appealing as it is likely to be more acceptable to the participant, may provide more consistent and functionally relevant data, and may reduce hospital attendances and healthcare costs. By utilizing biometric collection devices such as a pulse oximeter monitor with Bluetooth capability, telehealth can be used to capture the oxygen saturation levels in the blood from participants and transmit them to a secure server, allowing them to be reviewed by cardiologists and other healthcare professionals.

This study aims to compare the indoor 6MWT, with the hospital performed 6MWT. It will assess the feasibility and acceptance of a mobile phone app as an instrument to measure the 6MWT.

The 6MWT is currently undertaken at every Outpatient appointment, normally at 0- 3-, 6- and 12-month outpatient reviews. The participant would perform a hospital based 6MWT, whilst simultaneously using the indoor version of the app on their own mobile phone at baseline, 3- and 6-month follow up. This will demonstrate to the participant how to use the app, and we will be able to understand whether they are able to use it correctly. It will also allow direct comparison of the standard 6MWT distance measurement with the measurement provided by the app.

The participant will be then invited to use the app in their local environment, preferably in the outdoor scenario, and the collected information would then be transmitted to the hospital servers where it could be reviewed. The app could be used many times prior to attendance in outpatients, giving the clinicians more detailed information as to the overall functional status of the patient. Participants will be required to perform a test before and after their follow up appointments so that home-based measurements can be compared to hospital-based ones. They will be allowed to do as many tests as they are willing to, preferably once per week and at least each month.

Principal Investigator:

[name]

Short Title:

6-APP Study

Ethics Ref:

insert

In total, we aim to collect 3 indoor hospital-based measurements (baseline, 3- and 6-month) and at least 5 outdoor home measurements, one close to each hospital visit plus one between two visits. The data collected will allow us to understand the usage of the app by participants, validate the indoor measurements and correlate the home measurements with the hospital-based ones.

6. PARTICIPANT IDENTIFICATION

6.1. Study Participants

Participants with pulmonary arterial hypertension due to any cause who are able to perform a 6MWT. Patients on long term oxygen therapy will not be included as it will be difficult to perform the outside 6MWT whilst on oxygen. Also patients with cognitive impairments, even if able to use a smartphone, will be excluded as they would possibly introduce noise for not being able to use the app correctly.

6.2. Inclusion Criteria

- Participant is willing and able to give informed consent for participation in the study
- Male or Female, aged 18 years or above
- Diagnosed with PAH who are able to undertake 6MWT off-oxygen
- Being of PAH group 1 or 4
- Participant owns a compatible smartphone (Android or iPhone) and is able to use it.

6.3. Exclusion Criteria

The participant may not enter the study if ANY of the following apply:

- Long term oxygen therapy
- Cognitive impairments
- Rheumatological diseases that limit the measurement of finger Oxygen saturations
- PAH groups 2, 3 or 5
- Cannot use a smartphone
- Pregnancy.

7. STUDY PROCEDURES

7.1. Recruitment

Principal Investigator:	[name]	Ethics Ref:	insert
Short Title:	6-APP Study		

Patients undergoing follow up in the PAH clinic will be eligible for participation. They will be approached by a member of the clinical team for consideration and recruited. We will recruit 30 compliant patients to enrol in the study.

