7.2. Screening and Eligibility Assessment

The patients attending the PHT outpatient clinics will be screened to assess whether they have pulmonary arterial hypertension and assessed as to whether they will be able to undertake a 6MWT using the App and then recruited

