10.3. Analysis of Outcome Measures

All participants' data will be used excluding those who withdrew consent.

Primary Objective:

Principal Investigator:	[name]	Ethics Ref:	insert
Short Title:	6-APP Study		

O1: We will measure the percentage of participants who perform at least one home 6MWT between baseline visit and 3-month visit and the percentage of participants who perform at least one home 6MWT between baseline visit and 6-month visit. These two percentages will be used as the main measure of the success of this study.

In addition, the distribution over time of when home performed tests will be computed.

Secondary Objectives

O2: We will compute the mean and standard deviation of the difference in distance as measured by the physiologists and the app. To evaluate the agreement between the two approaches, a Bland Altman graph will be also prepared.

O3: We will compute the correlation of the distance as computed by the app when used at home within 3 days from the hospital visit with the one gathered in the hospital 6MWT test.

O4: Ease of use, acceptance and mobile phone affinity will be measured with standard questionnaires. Compliance with the use of the app will be measured by counting the frequency of use of the app. Simple descriptive statistics will be computed and correlations among quantities will be explored. A selected number of participants will be chosen for semi-structured interviews in order to gain a deeper understanding of their usage of the app.

Tertiary Objectives

O5: Descriptive statistics about the walked distance, blood oxygen saturation and heart rate, BORG scale and number of steps will be used to compare changes before and after initiation of new therapies.

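### O1 is worded for patients in general, but its percentage covers only consenting, app-capable smartphone owners, and no count of those who do not enter is planned

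*Combined protocol and SAP*

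**What the plan says.** Section 4 gives the primary objective as "To demonstrate that patients are able and willing to use the app for the 6MWT", and the Synopsis says the same. Section 10.3 defines the measure: "We will measure the percentage of participants who perform at least one home 6MWT between baseline visit and 3-month visit", with a matching percentage to 6 months. It adds that "These two percentages will be used as the main measure of the success of this study". The analysis set is given as "All participants' data will be used excluding those who withdrew consent".

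A clinic patient becomes a participant through several steps.

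- Section 7.1: "They will be approached by a member of the clinical team for consideration and recruited". The same section describes the 30 to be recruited as compliant.
- Section 6.2 requires informed consent, and also: "Participant owns a compatible smartphone (Android or iPhone) and is able to use it".
- Section 6.3 excludes anyone who cannot use a smartphone.
- Section 6.1 says that patients with cognitive impairments, including those who can use a smartphone, "will be excluded as they would possibly introduce noise for not being able to use the app correctly".
- Section 7.2 says that patients are "assessed as to whether they will be able to undertake a 6MWT using the App and then recruited".

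Sections 7.1 and 7.2 describe approach and screening without a log. Sections 10.1 to 10.3 plan no analysis of people who were considered but not enrolled. The study flow chart in Appendix A is not reproduced in the available text, so nothing is inferred from its absence.

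**The concern.** The objective concerns two traits, ability and willingness. Entry selects on both before counting begins. A patient who declines because of the app, has no compatible phone, or is judged unable to use the app is never in the denominator. These are direct instances of what O1 sets out to measure.

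Section 5 presents the study as evaluating a new way of delivering a service to PAH patients, and Section 3 foresees later use in other cardiorespiratory conditions. A reader weighing either will want to know what share of suitable clinic patients can and will use the app. Under the present plan the final report could give a high O1 percentage with no means of telling whether it came from most of the clinic or from a small, willing part of it. If the information is not recorded when each patient is first considered, it probably cannot be recovered later.

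This loss occurs before consent. It is separate from the handling of failure to use the app at the baseline visit (Section 7.4) and from the replacement of participants who withdraw (Section 7.6). Settling those would not recover it.

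**Working it through.** **Nothing to reproduce.** Section 10.2 gives 30 participants and states that no sample size calculation is provided. The documents give no target percentage, success threshold or number approached.

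**Inputs**

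- Enrolled: 30 (Synopsis, Section 10.2).
- Enrolled patients with at least one home test: 27, assumed for illustration.
- N, the number of otherwise suitable clinic patients screened to enrol 30: assumed 40, 60 or 100.
- f, the share of non-entrants kept out for app- or phone-related reasons: unknown, from 0 to 1.

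**Step 1: O1 as planned.** O1 = 27/30 = 90.0%, exact (Clopper-Pearson) 95% interval 73.5% to 97.9%. N does not appear in the formula, so the result is the same for any N. The interval describes sampling error among the enrolled and does not reflect selection into the study.

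**Step 2: all screened patients as denominator.** The share is 27/N. It counts every non-entrant as unable or unwilling, so it is a lower bound.

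| N screened | 27/N | Exact 95% interval |
|---|---|---|
| 40 | 67.5% | 50.9% to 81.4% |
| 60 | 45.0% | 32.1% to 58.4% |
| 100 | 27.0% | 18.6% to 36.8% |

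**Step 3: only app- or phone-related non-entry added.** The share is 27/(30 + f(N − 30)). With f = 1 it equals the figure in Step 2, and with f = 0 it equals 90.0%. With f = 0.5, chosen only as a midpoint:

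- N = 40: 27/(30 + 5) = 27/35 = 77.1%
- N = 60: 27/(30 + 15) = 27/45 = 60.0%
- N = 100: 27/(30 + 35) = 27/65 = 41.5%

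**Step 4: the best possible O1.** If all 30 do a home test, O1 is 100% (exact 95% interval 88.4% to 100%). Over all screened, the lower bounds are 30/40 = 75.0%, 30/60 = 50.0% and 30/100 = 30.0%. Even a perfect result does not settle the question as the objective words it.

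The distance between O1 and the figure for suitable clinic patients thus depends on N and f, and the plan records neither.

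**The case against.** The strongest reply is that the outcome is openly conditional. It is defined over participants, Section 6 says who they are, and nothing promises a clinic-wide uptake figure. The study is described as exploratory, no test or threshold rests on O1, and every consented feasibility study is conditional on consent. Restricting entry to smartphone owners is also a legitimate choice. All of this stands, and it limits the point to a mismatch between objective and denominator together with a missing count. It does not remove the point: the objective is stated for patients, and Section 10.3 makes this percentage the main measure of success.

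A reader might infer that O1 says nothing about ability or willingness. The documents do not support that. Consent and phone ownership do not ensure that someone will do an unsupervised home walk over 3 or 6 months. O1 measures that behaviour, and it is supplemented by the timing of home tests, frequency of use, questionnaires and interviews.

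A reader might also infer that most unwillingness shows itself at approach and most inability at eligibility, or that true uptake lies between 27% and 67.5%. The documents contain no data on either. The screened numbers are assumptions, and patients may decline for reasons unconnected with the app.

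Finally, a count limited to patients approached would miss anyone passed over beforehand for lack of a phone, and repeat clinic visits could count one person several times. Both objections are sound, and the proposed log is defined to meet them.

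**Conclusion.** The point holds in a limited form. Followed exactly, the plan yields a percentage selected on the traits it is meant to measure. O1 is a usable estimate of home-test completion among consenting, app-capable smartphone owners. It cannot support the objective as worded for patients in general, because refusal, lack of a phone and inability found before entry leave it unchanged.

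The size cannot be known from the documents. Under the assumptions above, an O1 of 90% is compatible with a share among screened patients from 67.5% to 90% if 40 were screened, 45% to 90% if 60, and 27% to 90% if 100. The lower end of each range treats all non-entry as related to the app or phone, and the upper end treats none of it so. This is a change that should be made: it determines what the primary objective can conclude, and the missing information has to be collected from the first patient considered.

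**What to change.** Keep the exclusions as they are.

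- **Sections 7.1 and 7.2:** keep a screening log of every clinic patient with group 1 or 4 PAH who can do a 6MWT off oxygen. Count each patient once, at first consideration, whether or not they are then approached. Give one reason code: no compatible phone; cannot use a smartphone or the app; cognitive impairment; declined because of the app; declined for another reason; other exclusion; enrolled.
- **Section 10.3:** report these counts beside O1. Add a second completion percentage whose denominator is enrolled patients plus those not entered for app- or phone-related reasons. Cognitive impairment belongs with these, since Section 6.1 gives incorrect app use as the reason for that exclusion. Show unrelated refusals and other exclusions separately, outside this denominator.
- **Sections 4 and 10.3:** state the O1 conclusion for consenting, app-capable smartphone owners.

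The cost is a short log entry per patient, one table, and a second figure that may be less favourable than O1. The log also needs a way to recognise repeat attenders, since Section 5 describes several clinic reviews per patient. It would hold reasons for non-entry, including cognitive status, for people who have not consented, so it should carry no identifiers outside the clinical team and be described in the ethics submission.

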7.4. Baseline Assessments

The baseline assessment will be a standard 6MWT which measures resting heart rate and oxygen level at rest, the distance walked over 6 minutes, then the oxygen saturations and heart rate at end of the 6MWT. Prior to the initiation of the test, participants will be asked to download the app onto their personal mobile phones. Participants will also be asked to use the app in its indoor mode, while performing the test in hospital. Participants who are not able to either download the app or use it correctly will be unable to participate. We will be using the BORG questionnaire at the end of both the app test and the hospital 6MWT. The Borg Rating of Perceived Exertion (RPE) is a way of measuring physical activity intensity level. Perceived exertion is how hard a patient feels they are working. It is based on the physical sensations a person experiences during physical activity, including increased heart rate increased breathing rate, increased sweating, and muscle fatigue. Although this is a subjective measure, a person's exertion rating may provide a fairly good estimate of the actual heart rate during physical activity (11). During activity, the patient uses the Borg Scale to assign numbers as to how hard they think they are working. Participants will be provided with the questionnaire at the end of their

Principal Investigator:

[name]

Short Title:

6-APP Study

Ethics Ref:

insert

6MWT and are encouraged to complete the questionnaire by the app or by the hospital physiologist. The physiologists undertaking the test will measure the distance walked using the system website to record the measurement. This way all measurements will be digitally available in one place. At the end of the assessment, participants will be asked to perform a home-based 6MWT within 3 days of the visit and 1 home test per week, or, at least, one per month.

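### Section 7.1 recruits 'compliant' patients, an undefined condition absent from 6.2 and 6.3; on its plain meaning it selects on the behaviour O1 measures and would bias O1 upward by an unknown amount

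*Combined protocol and SAP*

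**What the plan says.** Section 7.1 (Recruitment) makes patients under follow-up in the PAH clinic eligible and has a member of the clinical team approach them. It then says: "We will recruit 30 compliant patients to enrol in the study". It does not say what compliant means, who judges it, or when.

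Section 6.2 requires, among other things, willingness to consent and a smartphone: "Participant owns a compatible smartphone (Android or iPhone) and is able to use it". Neither 6.2 nor 6.3 contains a compliance criterion.

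The primary objective O1 (section 4) is: "To demonstrate that patients are able and willing to use the app for the 6MWT". Its analysis in 10.3 begins: "We will measure the percentage of participants who perform at least one home 6MWT between baseline visit and 3-month visit", with a matching percentage up to the 6-month visit. Section 10.3 adds: "These two percentages will be used as the main measure of the success of this study".

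Compliance appears in two other places. Under O4, section 10.3 says: "Compliance with the use of the app will be measured by counting the frequency of use of the app". Section 7.6 lists significant non-compliance with what the study requires as a ground for discontinuing a participant.

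**The concern.** O1 asks whether patients will use the app at home, and 10.3 makes the answer the study's main measure of success. If patients are chosen because they are compliant, and compliance means using the app or doing what the study asks, the sample is conditioned on the outcome. The percentage then describes home use among compliant patients, while objective O1 speaks of patients in general.

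Such selection is hard to undo later. The protocol text describes no count of patients approached, declining, judged not compliant, or excluded by the app checks. The content of the Appendix A flow chart is not available, so whether it shows such counts cannot be checked. A confidence interval on O1 would not reveal the problem, because it reflects sampling error only.

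**Working it through.** **1. Nothing to reproduce.** Section 10.2 gives 30 participants with no sample size calculation, and 10.3 sets no target percentage. The question is one of selection.

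**2. What the word can mean.** The possible readings, set against the other sections:

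- *Expected to comply.* This fits the use of compliance in 10.3 and 7.6. Likely non-users are not enrolled, and O1 is biased upward.
- *Thirty who turn out to comply.* This fits the replacement of withdrawn participants in 7.6. Selection then acts after enrolment. Section 10.3 limits this route, because it keeps all participants' data except from those who withdrew consent. The route stays open if the percentage is taken over the 30 who complied, or if non-users withdraw consent.
- *Meeting the entry criteria, or agreeing to take part.* The word then adds nothing to 6.2 and 6.3, and there is no bias from it.

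**3. Formula.** The reference population is consenting patients who meet 6.2 and 6.3. Let q be the share of them who count as compliant, pc the home-test rate in that group, and pn the rate in the rest.

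- Rate in the reference population = q × pc + (1 − q) × pn
- Rate seen if only compliant patients are enrolled = pc
- Overstatement = (1 − q) × (pc − pn)

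The overstatement is zero if q = 1 or pc = pn, and positive whenever q is below 1 and pc exceeds pn.

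**4. Numbers.** The documents give none of q, pc or pn, so every input below is assumed.

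| q | pc | pn | Reference rate | Rate seen | Overstatement |
|---|---|---|---|---|---|
| any | 90% | 90% | 90% | 90% | 0 points |
| 0.9 | 80% | 60% | 0.72 + 0.06 = 78% | 80% | 2 points |
| 0.9 | 90% | 70% | 0.81 + 0.07 = 88% | 90% | 2 points |
| 0.7 | 90% | 50% | 0.63 + 0.15 = 78% | 90% | 12 points |
| 0.7 | 90% | 40% | 0.63 + 0.12 = 75% | 90% | 15 points |
| 0.6 | 90% | 30% | 0.54 + 0.12 = 66% | 90% | 24 points |
| 0.5 | 95% | 20% | 0.475 + 0.10 = 57.5% | 95% | 37.5 points |

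Every row but the first builds in a gap of at least 20 points between the groups. The table shows how the overstatement depends on the inputs and does not estimate it.

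**5. Sampling error for scale.** If 27 of 30 did a home test (90%), the Clopper-Pearson 95% interval is 73.5% to 97.9%. It takes no account of how the 30 were chosen.

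**6. Selection that remains without the word.** Section 7.2 has patients "assessed as to whether they will be able to undertake a 6MWT using the App and then recruited", and 7.4 says: "Participants who are not able to either download the app or use it correctly will be unable to participate". Both select on ability. As an illustration with assumed counts, take 27 users among 30 analysed (90%). If 3, 6 or 10 non-users had been excluded at these checks, the rate counting them would be 27/33 = 82%, 27/36 = 75% or 27/40 = 67.5%. Deleting 'compliant' from 7.1 does not touch this.

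**The case against.** The strongest reply is that a single undefined word is being given one meaning. Section 7.1 does not say that anyone screens for compliance, and its preceding sentences point to open recruitment from the clinic. This stands in part. A reader might infer that the clinical team passes over patients before consent, but the documents do not say who judges compliance or when. Nor do they show that anyone passed over would be an O1 failure: one home test in the period is enough to count as a success, and a patient seen as unreliable may well do one.

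A reader might also infer that patients who decline inflate O1. They do not enter it. Willingness to consent is the first criterion in 6.2, and O1 is a percentage of participants. Declining is ordinary consent selection, present with or without the word.

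It can also be said that the study is exploratory, with 30 participants and no success threshold. Section 10.2 uses that label to explain the absence of a sample size calculation; it does not explain selecting on the primary outcome. The innocent reading, that compliant means eligible, makes the word redundant and is itself a reason to remove it.

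**Conclusion.** The point holds as a defect of wording with a likely direction. On the plain meaning of 'compliant', supported by 10.3 and 7.6, section 7.1 selects on the behaviour O1 measures, before or after enrolment. O1 would be biased upward relative to all consenting patients who meet 6.2 and 6.3. This rests on two assumptions: that the word means more than 'eligible', and that patients regarded as compliant do more home tests than the others.

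The size is unknown. The range of 0 to 37.5 points comes entirely from assumed inputs. The stronger statement, that O1 will be too high by some stated amount, is not supported.

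**What to change.** In 7.1, delete 'compliant' and state that consecutive clinic attenders who meet 6.2 and 6.3 are approached until 30 are enrolled, with no judgement of expected compliance.

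As a supporting step, keep a non-identifying tally of:

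- patients approached;
- patients declining, with not wanting to use the app as one recorded reason;
- patients excluded by the app checks in 7.2 and in 7.4.

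Report these counts beside the O1 percentages. The tally does not correct O1, but it shows the reader the uptake and the selection on ability that 7.2 and 7.4 still impose.

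The cost is one sentence in 7.1 and a simple count kept by the clinical team. The downside is that O1 may be lower and home data sparser, which leaves fewer home tests to compare with hospital tests under O3.
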